12.2.3 Analysis of patient reported outcomes

12.2.3.1 Hypotheses and objectives

The hypotheses and measurement strategy focus on the fact that patients in the trial will be starting with significant decrements in HRQoL and high rates of symptoms at study entry (baseline) due to previous chemotherapy and local treatments (surgery with or without radiation therapy). All analyses of Patient Reported Outcomes will be conducted on ITT population as listed in [Table 14](#). Therefore, the following hypotheses are proposed, based on the expected toxicities of olaparib.

Primary hypothesis

Patients receiving olaparib may experience greater fatigue severity during treatment than those receiving placebo as measured by the FACIT-Fatigue scale at 6 and 12 months after randomisation.

Secondary hypotheses

- Patients receiving olaparib may experience greater GI symptoms (nausea, vomiting and diarrhea) severity during treatment than those receiving placebo as measured at 6 and 12 months after randomisation but no difference expected by 24 months after randomisation.
- There will be no difference in fatigue post discontinuation of study treatment as measured at 18 and 24 months.
- There will be no difference in QOL between the two treatment arms as measured by the global QOL score and other sub scales from the EORTC QLQ-C30 at 6, 12, 18 and 24 months after randomisation and patients will demonstrate improvements in functioning over time

Primary PRO objective

To determine the effect of olaparib on patient-reported fatigue at 6 and 12 months after randomisation as measured by the FACIT-Fatigue symptoms questionnaire.

Secondary PRO objectives

- To determine the effect of olaparib on patient-reported GI symptoms (nausea, vomiting and diarrhea) over time at 6, 12, 18 and 24 months as measured by the EORTC QLQ-C30 scale.
- To determine the effect of olaparib on patient reported fatigue over time at 6, 12, 18 and 24 months as measured by the FACIT-Fatigue questionnaire.
- To determine if there will be a difference in QOL between the two treatment groups over time as measured by the 2 item global QOL score of the EORTC QLQ-C30 scale at 6, 12, 18 and 24 months and assess if patients demonstrate improvement in scores over time.
- To examine and compare the effect of olaparib over time on different functional sub scale scores as measured by the EORTC QLQ-C30 and assess if patients demonstrate improvement in functioning over time, with particular interest in the physical and emotional sub scales.

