12.2.3.2 Statistical considerations for patient reported outcomes

Statistical analyses

Primary endpoint – Fatigue

For the primary hypothesis, the composite fatigue score (FACIT-Fatigue questionnaire) measured at 6 and 12 months after randomisation will be compared between the two treatment arms using analysis of covariance (ANCOVA) with adjustment for the corresponding baseline measurement. Separate analyses will be done for patients who have received prior neoadjuvant chemotherapy and patients who have received standard post-surgical adjuvant chemotherapy. Separate analyses are preferable because the timing of chemotherapy is expected to impact the fatigue outcome directly. Each comparison will be performed at the significance level of 0.05. No multiple comparisons adjustment will be employed since these outcomes evaluate the toxicity of the study treatment.

To further assess the effect of olaparib on fatigue over time (study treatment period and the year following) the composite fatigue score (FACIT-Fatigue questionnaire) measured at 6, 12, 18 and 24 months after randomisation will be compared between the two treatment arms using a mixed model for repeated measures (MMRM) analysis of all of the post baseline scores. The model will include treatment, time and treatment by time interaction as explanatory variables and baseline score and baseline by time interaction as covariates. The treatment by visit interaction will remain in the model regardless of significance. The adjusted mean change from baseline estimates for each treatment arm, difference in the adjusted mean change from baseline estimates between the arms and corresponding confidence intervals will be presented by time point. Plots of the adjusted means changes over time will also be presented.

Secondary PRO endpoints

A secondary analysis based on GI symptoms (nausea, vomiting and diarrhea) over time from the EORTC QLQ-C30 scale will be performed using the same MMRM model described above. The adjusted mean change from baseline estimates for each treatment arm, difference in the adjusted mean change from baseline estimates between the arms and corresponding confidence intervals will be presented by visit. Plots of the adjusted means changes over time will also be presented for nausea, vomiting and diarrhea.

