To assess if there are any difference in HRQoL, the 2 item global QOL score assessed by EORTC QLQ-30 measured at 6, 12, 18 and 24 months after randomisation will be compared between the two treatment arms using the same MMRM model described above. Plots over time will also be produced for the global QOL score.

In addition, other subscales of the EORTC QLQ-C30 will be analysed using the MMRM model described above with particular interest in the emotional and physical subscales. Plots over time will also be produced.

All secondary analyses are considered exploratory and therefore no adjustments for multiplicity will be made. For each comparison, p-values (along with CIs) will be generated to help aid interpretation of the results using a nominal significance level of 0.05 (2-sided).

Because this trial is being conducted internationally, responses to patient reported outcomes may be influenced by differences between country/language categories ([Bernhard J et al 2007](#)). Therefore, analyses will be stratified by country/language groups. Further details will be provided in the SAP.

Adjustment for previous treatment exposures (radiation, type of chemotherapy, and surgery) may also be considered as part of the secondary analyses. Further details will be given in the SAP.

Sample size consideration

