We assume that half of triple negative patients and a quarter of hormone receptor positive patients will have received neoadjuvant chemotherapy and we anticipate that 95% of patients enrolled in the trial will complete the HRQoL instrument. In addition, adjusting downward to allow for 20% of missing data at the 12 months assessment point, we expect that data from 633 neoadjuvant and 735 adjuvant patients will be available (assuming that 15% of the total 1800 enrolled patients are ER and/or PgR positive HER2 negative). These will be sufficient to provide statistical power of 93% and 96% correspondingly to detect a difference of 3 points on the FACIT-Fatigue scale score between treatment groups assuming a standard deviation of 10.9 ([Cella D et al 2002](#)) (estimated SD of mean baseline score) and controlling α -level at 0.05. The 3-point difference is the clinically meaningful difference reported by the developers of the scale ([Cella D et al 2002](#)), and we are hypothesizing that the olaparib arm will be worse. A collection of PROs and QOL from all patients enrolled in the main trial will give us sufficient statistical power to detect important differences between two treatment groups.

Missing PRO data

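### The secondary PRO hypotheses of no difference have no criterion that could support them, and the MMRM leaves out the randomisation factors (minor point)

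*Protocol*

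**What the plan says.** Among the secondary PRO hypotheses in Protocol section 12.2.3.1 are two that assert sameness. For fatigue: "There will be no difference in fatigue post discontinuation of study treatment as measured at 18 and 24 months". For EORTC QLQ-C30: "There will be no difference in QOL between the two treatment arms as measured by the global QOL score" and the other subscales, at 6, 12, 18 and 24 months. The matching objective in the same section is neutral: "To determine if there will be a difference in QOL between the two treatment groups over time".

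Section 12.2.3.2 sets the analysis. Fatigue over time, global QOL and the other subscales are all compared with one MMRM, whose terms are listed: "The model will include treatment, time and treatment by time interaction as explanatory variables and baseline score and baseline by time interaction as covariates". Differences in adjusted mean change between the arms are to be reported with confidence intervals. On interpretation: "For each comparison, p-values (along with CIs) will be generated to help aid interpretation of the results", at a nominal two-sided 0.05. On status: "All secondary analyses are considered exploratory and therefore no adjustments for multiplicity will be made".

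The sample size paragraph of the same section powers FACIT-Fatigue for a 3-point difference with SD 10.9 and says of that figure: "The 3-point difference is the clinically meaningful difference reported by the developers of the scale". The protocol gives no equivalence or non-inferiority margin for any PRO scale, and no SD or meaningful difference for QLQ-C30.

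Randomisation is stratified by hormone receptor status, neoadjuvant versus adjuvant chemotherapy, and prior platinum (section 5.2.3). None of these is in the MMRM list. The primary fatigue ANCOVA adjusts for baseline and is run separately by chemotherapy setting, because timing of chemotherapy is expected to affect fatigue directly.

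**The concern.** A hypothesis of no difference cannot be supported by a test whose null is no difference. If the p-value exceeds 0.05, the data may still be compatible with a difference that matters. If it falls below 0.05 in a sample this large, the difference may be too small to matter. The hypothesis, the neutral objective and the test therefore do not line up, and the text names no result that would count as support.

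This has some practical weight. Section 3.2.2 gives the purpose of the PRO work as learning whether olaparib slows recovery after primary treatment. After a 12-month adjuvant course, readers will look for a statement about lasting effects at 18 and 24 months, and the plan should say in advance what would justify one.

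The second, separate matter is the model. The three factors used to stratify the randomisation are absent from the MMRM terms, although the protocol itself expects one of them to influence fatigue.

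**Working it through.** **Inputs (section 12.2.3.2, sample size consideration).** 1800 patients; 95% complete the instrument; 20% missing at 12 months; 15% hormone receptor positive; neoadjuvant chemotherapy in half of triple-negative and a quarter of hormone receptor positive patients; SD 10.9; difference 3 points; α 0.05. Allocation is 1:1.

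**Reproducing the protocol's figures.**
- Evaluable: 1800 × 0.95 × 0.80 = 1368.
- Neoadjuvant share: 0.85 × 0.5 + 0.15 × 0.25 = 0.4625, giving 632.7 neoadjuvant and 735.3 adjuvant (stated 633 and 735).
- Power = Φ(3/SE − 1.96), with SE = 10.9 × √(4/n). For n = 633, SE = 0.866 and power is 93.3%. For n = 735, SE = 0.804 and power is 96.2%. The stated 93% and 96% are confirmed.

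**What the difference test says about a no-difference hypothesis (FACIT-Fatigue).** For all 1368 patients, SE = 10.9 × √(4/1368) = 0.589 and the 95% CI half-width is 1.96 × 0.589 = 1.16.
- Significant although small: an observed difference of 1.16 points reaches p = 0.05. A true difference of 1.5 points, half the clinically meaningful value, gives p < 0.05 with probability Φ(1.5/0.589 − 1.96) = 72%.
- Not significant although real: a true 2-point difference gives p > 0.05 with probability 36% at n = 633, 30% at n = 735 and 8% at n = 1368.

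**What the planned CI could say once a margin is named.** The chance that the 95% CI lies wholly within ±3 when the true difference is zero is 2Φ(3/SE − 1.96) − 1.

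| n | CI half-width | Chance that CI lies within ±3 |
|---|---|---|
| 633 (neoadjuvant) | 1.70 | 86.7% |
| 735 (adjuvant) | 1.58 | 92.3% |
| 1368 (all) | 1.16 | 99.8% |

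The 1368 is a 12-month figure. Numbers at 18 and 24 months are not stated and are likely to be lower, since PRO collection stops after recurrence or a second primary (section 6.5.3). At an assumed 1100 the half-width is 1.96 × 10.9 × √(4/1100) = 1.29.

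**QLQ-C30 global score.** The protocol gives neither an SD nor a margin. Assuming SD 20 to 25 and 684 per arm, the half-width is 2.1 to 2.7 points. The corresponding chance of a CI within the margin is 92 to 99% at ±5, 68 to 92% at ±4 and 21 to 58% at ±3. What could be concluded therefore depends heavily on a margin that is not stated.

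**Randomisation factors.** If they explain a share R² of residual variance, including them multiplies the SE by √(1 − R²): 0.995 at R² = 0.01 and 0.949 at R² = 0.10, a reduction of about 0.5 to 5%. The R² range is an assumption. As an illustration, on the stated power calculation the same range would move 93.3% to 93.6–95.4% and 96.2% to 96.3–97.6%.

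**The case against.** The strongest reply is that nothing in the protocol turns p > 0.05 into a finding of no difference. Confidence intervals are required alongside the p-values, which are there only to help interpretation. The secondary PRO analyses are declared exploratory, and section 12.2.5 names only DDFS and OS as secondary endpoints intended for label claims. The hypotheses are introduced as resting on expected toxicities, so they can be read as expectations. All of this stands and sets the weight of the point. It does not supply the missing criterion: the exploratory label is given as the reason for not adjusting for multiplicity, not as a way of reading a difference test as evidence of sameness.

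A reader might infer that the trial cannot support any quality-of-life conclusion. The documents do not support that. No confirmatory QOL claim is made, and for fatigue the planned intervals are narrow enough to exclude a 3-point difference.

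It is also fair that the 3 points enter the protocol as the effect size for a superiority calculation, not as a margin. Using them as one is a choice, though it rests on the protocol's own description of what is clinically meaningful.

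On the model, one might say that covariates belong to the SAP. Section 12.2.3.2 does defer country/language stratification and possible adjustment for prior radiation, chemotherapy type and surgery. The MMRM terms, however, are listed outright, and those deferrals do not cover the randomisation factors. A reader might also infer that leaving them out biases the comparison. It does not: with 1:1 randomisation and baseline adjustment, the cost is a little precision.

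**Conclusion.** The point holds as a minor one. The no-difference hypotheses are paired only with tests for a difference and have no stated criterion by which they could be supported. For FACIT-Fatigue the gap between significant and meaningful is wide: about 1.2 points against 3 with all 1368 patients. The same planned interval, read against ±3, would meet the criterion in 99.8% of trials if there were truly no difference.

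These figures rest on the protocol's SD of 10.9, its 12-month evaluable number and a pooled analysis. Fewer patients at 18 and 24 months would widen the interval, and adjustment for baseline would tend to narrow it. For QLQ-C30 the figures rest wholly on assumed SDs and margins.

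The missing randomisation factors are a separate refinement, worth about 0.5 to 5% of the SE under the assumed R², and they play no part in the margin problem.

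**What to change.** 1. **FACIT-Fatigue at 18 and 24 months.** State that absence of a meaningful difference will be concluded only if the planned 95% CI for the difference between arms lies within ±3 points.
2. **QLQ-C30.** Either name a margin for the global score, and for any subscale on which sameness is to be asserted, before unblinding; or reword the hypothesis as an expectation and report estimates with CIs, in line with the neutral objective in the same section.
3. **Model terms.** Add hormone receptor status, chemotherapy setting and prior platinum to the MMRM, and hormone receptor status and prior platinum to the ANCOVA within each chemotherapy setting.

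The cost is a few sentences in the protocol or SAP, agreement on a QLQ-C30 margin if that route is taken, and a few degrees of freedom. No data collection, sample size or stated power changes.

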12.2.3.2 Statistical considerations for patient reported outcomes

Statistical analyses

Primary endpoint – Fatigue

For the primary hypothesis, the composite fatigue score (FACIT-Fatigue questionnaire) measured at 6 and 12 months after randomisation will be compared between the two treatment arms using analysis of covariance (ANCOVA) with adjustment for the corresponding baseline measurement. Separate analyses will be done for patients who have received prior neoadjuvant chemotherapy and patients who have received standard post-surgical adjuvant chemotherapy. Separate analyses are preferable because the timing of chemotherapy is expected to impact the fatigue outcome directly. Each comparison will be performed at the significance level of 0.05. No multiple comparisons adjustment will be employed since these outcomes evaluate the toxicity of the study treatment.

To further assess the effect of olaparib on fatigue over time (study treatment period and the year following) the composite fatigue score (FACIT-Fatigue questionnaire) measured at 6, 12, 18 and 24 months after randomisation will be compared between the two treatment arms using a mixed model for repeated measures (MMRM) analysis of all of the post baseline scores. The model will include treatment, time and treatment by time interaction as explanatory variables and baseline score and baseline by time interaction as covariates. The treatment by visit interaction will remain in the model regardless of significance. The adjusted mean change from baseline estimates for each treatment arm, difference in the adjusted mean change from baseline estimates between the arms and corresponding confidence intervals will be presented by time point. Plots of the adjusted means changes over time will also be presented.

Secondary PRO endpoints

A secondary analysis based on GI symptoms (nausea, vomiting and diarrhea) over time from the EORTC QLQ-C30 scale will be performed using the same MMRM model described above. The adjusted mean change from baseline estimates for each treatment arm, difference in the adjusted mean change from baseline estimates between the arms and corresponding confidence intervals will be presented by visit. Plots of the adjusted means changes over time will also be presented for nausea, vomiting and diarrhea.

To assess if there are any difference in HRQoL, the 2 item global QOL score assessed by EORTC QLQ-30 measured at 6, 12, 18 and 24 months after randomisation will be compared between the two treatment arms using the same MMRM model described above. Plots over time will also be produced for the global QOL score.

In addition, other subscales of the EORTC QLQ-C30 will be analysed using the MMRM model described above with particular interest in the emotional and physical subscales. Plots over time will also be produced.

All secondary analyses are considered exploratory and therefore no adjustments for multiplicity will be made. For each comparison, p-values (along with CIs) will be generated to help aid interpretation of the results using a nominal significance level of 0.05 (2-sided).

Because this trial is being conducted internationally, responses to patient reported outcomes may be influenced by differences between country/language categories ([Bernhard J et al 2007](#)). Therefore, analyses will be stratified by country/language groups. Further details will be provided in the SAP.

Adjustment for previous treatment exposures (radiation, type of chemotherapy, and surgery) may also be considered as part of the secondary analyses. Further details will be given in the SAP.

Sample size consideration

We assume that half of triple negative patients and a quarter of hormone receptor positive patients will have received neoadjuvant chemotherapy and we anticipate that 95% of patients enrolled in the trial will complete the HRQoL instrument. In addition, adjusting downward to allow for 20% of missing data at the 12 months assessment point, we expect that data from 633 neoadjuvant and 735 adjuvant patients will be available (assuming that 15% of the total 1800 enrolled patients are ER and/or PgR positive HER2 negative). These will be sufficient to provide statistical power of 93% and 96% correspondingly to detect a difference of 3 points on the FACIT-Fatigue scale score between treatment groups assuming a standard deviation of 10.9 ([Cella D et al 2002](#)) (estimated SD of mean baseline score) and controlling α -level at 0.05. The 3-point difference is the clinically meaningful difference reported by the developers of the scale ([Cella D et al 2002](#)), and we are hypothesizing that the olaparib arm will be worse. A collection of PROs and QOL from all patients enrolled in the main trial will give us sufficient statistical power to detect important differences between two treatment groups.

Missing PRO data

A certain amount of missing data is expected. If data for individual items are missing, imputation will be done as follows: if less than 50% of the subscale items were missing (e.g. at most 2 out of 5 items, etc), the subscale score based on the non-missing items will be divided by the number of non-missing items and multiplied by the total number of items on the subscale. If at least 50% of the items are missing, that subscale will be treated as missing (not evaluable). If the scale is a single-item measure, a missing value will automatically be defined as 'Non-Evaluable'. The information from patients with missing data will be reviewed in order to determine whether data analytic procedures are likely to be biased. Patients with missing data will be reviewed for imbalances in factors such as trial arm, treatment adherence, institution, and reason for non-adherence. When QOL data are missing at a particular time point, data from prior time points will be reviewed in order to investigate whether missing status was preceded by a significant change in QOL scores. In addition, we will investigate whether missing item status is related to other scores on the same questionnaire. If no missing data mechanism can be detected following this review, the data will be analysed assuming the data are missing at random. If, on the other hand, a missing data mechanism appears to be present, we will undertake to develop an appropriate analytic strategy to control for the potential bias and, if possible, to impute the missing values. We will also present sensitivity analyses based on varying assumptions about the missing-data mechanism.

Full details on the analysis and derivation of PRO endpoints will be provided in the statistical analysis plan (SAP).

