This is a collaborative study being coordinated worldwide by the Breast International Group (BIG) in partnership with Frontier Science (FS), NRG Oncology (NCI supported National Clinical Trials Network Group) and AstraZeneca (AZ). Two versions of this protocol have been written to cover this global adjuvant breast cancer study. One protocol version covers all patients recruited outside of the US (where AZ is the sponsor) and one protocol version covers patients recruited within the US (where NRG Oncology is the sponsor). The two versions of the protocol are identical in terms of study objectives and scientific content and only differ in logistical content appropriate for the country(ies) they cover (i.e. drug distribution, mechanisms for SAE reporting during the study, etc.). Based on current recruitment rates, it is expected that approximately 230 patients will be randomised under the US protocol and approximately 1570 patients will be randomised under the Rest of the World protocol.

The trial will use one randomisation system and report as one single study. The initial collection of the patients' data will be done using two databases (one for the US patients and one for all other patients outside of the US). The two databases will be set up using the same standards and eCRFs to ensure consistency in the data collection. The data from both databases will be combined into a single consolidated database at regular, pre-specified intervals. All study endpoints as well as reports for periodic review by the Independent Data Monitoring Committee

(IDMC) will be analysed and reported from the single combined reporting database held by Frontier Science on behalf of BIG.

Study design

This is a randomised, double-blind, parallel group, placebo-controlled multi-centre Phase III study to assess the efficacy and safety of olaparib versus placebo as adjuvant treatment in patients with germline *BRCA1/2* mutations and high risk HER2 negative primary breast cancer who have completed definitive local treatment and neoadjuvant or adjuvant chemotherapy.

Patients will be randomised in a 1:1 ratio to either olaparib or placebo. Randomisation will be stratified by hormone receptor status (ER and/or PgR positive/HER2 negative versus TNBC), by prior neoadjuvant versus adjuvant chemotherapy, and prior platinum use for breast cancer (yes versus no).

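### The primary fatigue ANCOVA adjusts for baseline only, so its 12-month estimate can be biased under missing at random if dropout follows 6-month fatigue and differs between arms; the MMRM already planned should be primary

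*Protocol*

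**What the plan says.** Protocol 12.2.3.1 makes fatigue at 6 and 12 months the primary PRO objective and places all PRO analyses on the ITT population. For this objective 12.2.3.2 states that the FACIT-Fatigue score "will be compared between the two treatment arms using analysis of covariance (ANCOVA) with adjustment for the corresponding baseline measurement", in separate analyses of the neoadjuvant and adjuvant groups. It adds: "Each comparison will be performed at the significance level of 0.05". No multiplicity adjustment is made.

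To describe fatigue over the longer period, the same section adds a comparison of the 6-, 12-, 18- and 24-month scores "using a mixed model for repeated measures (MMRM) analysis of all of the post baseline scores". That model has treatment-by-time and baseline-by-time terms and reports between-arm differences with confidence intervals at each time point. Its paragraph does not mention the neoadjuvant/adjuvant split.

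The sample size paragraph works by "adjusting downward to allow for 20% of missing data at the 12 months assessment point". The missing-data paragraph gives an imputation rule for single missing items and treats a subscale as not evaluable if at least half its items are missing. It then describes a review of missingness, including by trial arm and by change in earlier scores: "If no missing data mechanism can be detected following this review, the data will be analysed assuming the data are missing at random". If a mechanism does appear, an analytic strategy is to be developed and values imputed where possible. Sensitivity analyses under varying assumptions are promised in addition.

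**The concern.** An ANCOVA of the 12-month score on arm and baseline gives a valid comparison among responders only if, given arm and baseline, responding is unrelated to the 12-month score. Missing at random is a weaker condition. It lets missingness depend on anything observed, including the 6-month fatigue score, and the plan's own review anticipates that link. The named primary analysis cannot use that score, whereas the MMRM in the same section can.

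Fatigue is the side effect that 3.2.2 calls the most frequent with olaparib. If patients on olaparib who are more fatigued at 6 months are less likely to return the 12-month form, the primary comparison is made among a less fatigued remainder and understates a toxicity. The primary result could then disagree with the protocol's own MMRM at the same visit.

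**Working it through.** **1. The plan's own figures reproduce.** Inputs from 12.2.3.2: 1800 patients, 15% hormone receptor positive (270, leaving 1530 TNBC), half of TNBC and a quarter of hormone receptor positive patients neoadjuvant, 95% completing the instrument, 20% missing at 12 months, SD 10.9, difference 3 points.

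- Neoadjuvant: (1530 × 0.5 + 270 × 0.25) × 0.95 × 0.80 = 832.5 × 0.76 = 632.7 (stated 633).
- Adjuvant: (1530 × 0.5 + 270 × 0.75) × 0.95 × 0.80 = 967.5 × 0.76 = 735.3 (stated 735).
- Power, two-sided 5%: Φ(3 / (10.9 × √(4/n)) − 1.96). For n = 633 this is Φ(3.462 − 1.96) = 93.3%; for n = 735 it is Φ(3.731 − 1.96) = 96.2% (stated 93% and 96%). A one-sided test would give 96.5% and 98.2%, so the stated figures are two-sided.

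**2. Who is in the ANCOVA.** The text does not say. Three features point to visit responders only: power is computed on patients with 12-month data, imputation is defined for single items only, and no rule is given for a wholly missing questionnaire.

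**3. Why the 6-month score matters.** Write the 12-month score as linear in arm, baseline and 6-month score. Among responders, the baseline-only ANCOVA is then shifted by c × (S_olaparib − S_placebo). Here c is the coefficient of the 12-month score on the 6-month score given baseline, and S is the amount by which the mean 6-month score of 12-month responders differs from that of all patients with the same baseline. With equal SDs, c = (r6,12 − r0,6 × r0,12) / (1 − r0,6²). For the two assumed correlation sets (r0,6 / r0,12 / r6,12):

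- 0.5/0.4/0.6: (0.6 − 0.20) / 0.75 = 0.53
- 0.6/0.5/0.7: (0.7 − 0.30) / 0.64 = 0.63

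Selection alone therefore does no harm. It must differ between arms.

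**4. Size, by simulation.** From the plan: SD 10.9, true difference 3 points, about 20% missing at 12 months. Assumed, because the protocol gives none of these: the correlations above, trivariate normal scores, the dropout slopes (log-odds of missing per SD of 6-month fatigue), and the split of missingness by arm. Each scenario used 600,000 patients (Monte Carlo error about 0.03 points). The comparator is the likelihood estimate that also uses the 6-month score, equivalent here to an unstructured MMRM. Each cell gives the two correlation sets in order.

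| 12-month dropout | ANCOVA | Using 6-month score |
|---|---|---|
| Unrelated to score | 2.95, 2.99 | 2.95, 2.99 |
| Common model, slope 0.5 | 2.96, 3.02 | 2.99, 3.06 |
| Common model, slope 1.0 | 2.86, 2.89 | 2.99, 3.02 |
| Common model, slope 1.5 | 2.76, 2.77 | 2.99, 3.00 |
| Slope 1.0 in both arms, 15% placebo v 25% olaparib missing | 2.60, 2.63 | 2.96, 3.00 |
| Olaparib only, slope 0.5 | 2.58, 2.58 | 3.01, 3.00 |
| Olaparib only, slope 1.0 | 2.23, 2.21 | 2.99, 2.99 |

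Further runs gave 2.63 to 2.65 for slopes of 1.0 on olaparib and 0.5 on placebo with 20% missing in each arm, about 2.7 on repeating the 15% v 25% case, and 3.0 with equal slopes and equal missing rates.

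With no true difference, ANCOVA is unbiased under a common dropout model (−0.01). It favours olaparib by 0.38 to 0.40 points with 15% v 25% missing, and by 0.74 to 0.78 points with olaparib-only dropout at slope 1.0.

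**5. Effect on power.** If the quantity ANCOVA estimates shrinks to 2.75, 2.5 or 2.25 points, the formula in step 1 gives 89%/93%, 82%/88% or 74%/80% (neoadjuvant/adjuvant).

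**The case against.** The case for leaving the plan alone has real substance.

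- Missing at random allows bias here but does not imply it. The larger losses need dropout that differs by arm, and the slopes, correlations and arm splits are all assumed. This stands, and it sets the wording of the point.
- The plan is not blind to the problem. It adopts missing at random only after a review that looks at trial arm and at earlier changes in score, with a fallback strategy and sensitivity analyses. This stands in part. The fallback and the sensitivity methods are unspecified, a review can miss a mechanism, and the primary method would be chosen after the missing data had been seen.
- The MMRM will report the 12-month contrast anyway, and fatigue lies outside the error-controlled hierarchy of 12.2.5. This stands as a limit on severity: the weakness is which analysis is called primary. However, no split by chemotherapy setting is stated for the MMRM, although 12.2.3.2 prefers separate analyses for the primary hypothesis.
- Handling of wholly missing questionnaires may be set out in the SAP. That is fair, and use of visit responders only remains an inference. The choice of a baseline-only ANCOVA as primary is nevertheless fixed in the protocol.
- Under 6.5.3, patients who stop drug for reasons other than recurrence or a second primary are expected to continue questionnaires, so stopping for toxicity does not itself end collection. Collection does end at recurrence or second primary cancer, which could differ by arm in the opposite direction. This stands: the direction of any bias is plausible, not assured.

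A reader might infer that the whole primary fatigue analysis is biased. The documents do not support that. At 6 months there is no earlier post-baseline score to leave out, and at 12 months bias depends on a dropout pattern that the protocol neither states nor predicts.

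**Conclusion.** The point holds in a limited form. Read as an analysis of visit responders, the primary 12-month fatigue comparison is not generally valid under the missing-at-random assumption that the plan adopts conditionally, while a model that is valid under it sits in the same section in a supporting role.

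Of a true 3 points, the 12-month ANCOVA would recover about 2.2 to 2.7 if dropout by fatigue differs between arms, about 2.75 to 3.0 under one common dropout model, and all 3 if missingness is unrelated to the score. These sizes rest on about 20% missing, the two assumed correlation sets and the assumed slopes. The estimates that use the 6-month score (2.95 to 3.06) are unbiased within simulation error because every scenario was missing at random by construction. They say nothing about dropout driven by fatigue arising after month 6.

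This is a cheap improvement worth making, not an error that invalidates the PRO plan. It gives no reason to change the stated sample size or power.

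**What to change.** In 12.2.3.2, name the 6- and 12-month treatment contrasts from the MMRM already specified as the primary fatigue analysis, fitted within the neoadjuvant and adjuvant groups. Keep the visit-wise ANCOVA as supportive. State which patients enter each analysis.

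The cost is wording in the protocol and SAP, with no new data. The drawback is that the primary result then rests on a repeated-measures model. That model does not remove missing-not-at-random bias, and it implicitly extrapolates scores that are not collected after recurrence or second primary cancer. The planned sensitivity analyses are therefore still needed, and their methods should be fixed before the missing data are reviewed.
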